7.3.2. Subgroup Analyses for Primary Endpoint

Subgroups will be formed based on the following participant characteristics and baseline variables for those participants whose data are available:

- Sex: male and female
- Age group: ≤ 65 years or > 65 years
- MF type: PMF or PPV-MF/PET-MF
- Presence/absence of V617F mutation at baseline
- Presence/absence of HMR mutations at baseline
- Baseline spleen volume group: \leq median or $>$ median
- Baseline spleen palpation size group: ≤ 10 cm or > 10 cm
- Race: White/Caucasian, Black/African-American, Asian, American-Indian/Alaska Native, Native Hawaiian/Pacific Islander, or other
- Ethnicity: Hispanic/Latino, not Hispanic/Latino, or other
- Platelet: $\geq 100 \times 10^9/L$ vs 50 to $< 100 \times 10^9/L$, inclusive using baseline platelet counts. Note that if a participant's platelet count is $< 50 \times 10^9/L$ at baseline, the platelet count at screening will be used for stratification/randomization.
- DIPSS: intermediate-1, intermediate-2, or high

7.3.3. Sensitivity and Supportive Analyses for Primary Endpoint

The primary endpoint will be analyzed using the PP population as a sensitivity analysis to the ITT population.

The participants who make an early crossover and later turn into responders will be considered responders and analyzed in the placebo group as a supportive analysis.

7.4. Analysis of the Secondary Efficacy Parameters

7.4.1. Spleen Volume Reduction

7.4.1.1. Time to the First $\geq 35\%$ Reduction in Spleen Volume

The time to the first $\geq 35\%$ reduction in spleen volume is defined as the time from randomization to the first time participants had $\geq 35\%$ reduction in spleen volume. Participants with baseline and postbaseline MRI or CT scan who do not have $\geq 35\%$ reduction in spleen volume at the time of analysis will be censored at the time of the last MRI or CT scan. If the participants have no baseline or postbaseline MRI or CT scan, they will be censored at the date of randomization.

The stratified log-rank test will be used to compare time to the first $\geq 35\%$ reduction in spleen volume between 2 treatment groups in the ITT population at a 1-sided 2.5% significance level, stratified for baseline (or screening, if applicable) platelet count and DIPSS category. The strata identified in the randomization process will be used for the analysis.

Kaplan-Meier curves for time to the first $\geq 35\%$ reduction in spleen volume will be presented by treatment groups. The KM estimate of median time to the first $\geq 35\%$ reduction in spleen volume will be presented with its 95% CI. The 95% CI will be calculated using the generalization of method of Brookmeyer and Crowley (1982) with log-log transformation (Klein and Moeschberger 1997).

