OS adjusted for crossover using rank preserving structural failure time	Inference: Cox regression model including treatment group, baseline (or screening, if applicable) platelet count ($\geq 100 \times 10^9/L$ vs 50 to $< 100 \times 10^9/L$ inclusive), and DIPSS category (intermediate-1 vs intermediate 2 vs high) at randomization	ITT	S
Time to the first $\geq 35\%$ reduction in spleen volume	Inference: Log-rank test with stratification of baseline (or screening, if applicable) platelet count ($\geq 100 \times 10^9/L$ vs 50 to $< 100 \times 10^9/L$ inclusive) and DIPSS (intermediate-1 vs intermediate-2 vs high) at randomization Estimation: Kaplan-Meier	ITT	P
Duration of maintenance of a $\geq 35\%$ reduction in spleen volume	Estimation: Kaplan-Meier	ITT with spleen response	P

Other secondary endpoints, including change and percentage change in MFSAF TSS over time from baseline to Week 24 as measured by the MFSAF v4.0 diary, will be summarized descriptively by treatment group.

For the stratifications of platelet and DIPSS, within a platelet category, in the event that a particular DIPSS stratification level has fewer than 30 participants randomized, it will be combined with the nearest adjacent DIPSS level (eg, Intermediate-1 vs Intermediate-2 vs High). For example, if too small, Intermediate-1 or High risk will be merged with Intermediate-2. If Intermediate-2 has too few participants, then it will be merged with the smaller of the 2 adjacent strata.

In the event that 2 DIPSS stratification levels are combined, a sensitivity analysis for the primary endpoint without combining levels will be conducted.

The primary endpoint will also be compared between treatment groups within each of the following subgroups:

- Baseline platelet count ($\geq 100 \times 10^9/L$ vs 50 to $<100 \times 10^9/L$ inclusive) (Note that if a participant's platelet count is $< 50 \times 10^9/L$ at baseline, the platelet count at screening will be used instead)
- DIPSS category (Intermediate-1 vs Intermediate-2 vs High)
- Sex: male and female
- Age group: ≤ 65 years or > 65 years
- MF type: PMF or PPV-MF/PET-MF
- Presence/absence of V617F mutation at baseline
- Presence/absence of HMR mutations at baseline
- Baseline spleen volume group: \leq median or $>$ median
- Baseline spleen palpation size group: ≤ 10 cm or > 10 cm
- Race: white/Caucasian, black/African American, Asian, American Indian/Alaska Native, Native Hawaiian/Pacific Islander, or other

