3.2. Control of Type I Error

This study defines a single primary endpoint with a single primary analysis. The study will be claimed to have achieved the primary efficacy objective when the primary endpoint shows a significant result at 2-sided alpha of 0.05 at final analysis. The secondary efficacy endpoints will be analyzed only when the study has reached the efficacy objective in the primary endpoint. The key secondary efficacy variables will be tested following a fixed-sequence-testing procedure with each at the 2-sided alpha level of 0.05 in the order below:

1. The proportion of participants who have a $\geq 50\%$ reduction from baseline to Week 24 in MFSAF TSS
2. Overall survival

Other secondary [REDACTED] endpoints will be tested using a 2-sided, 5% significance level; however, these are not considered alpha-controlled hypotheses.

There are 2 planned interim analyses in this study, both aiming to terminate the study if there is inadequate efficacy. The nonbinding futility rules in Interim Analyses 1 and 2 will control the probability of continuing beyond Interim Analysis 2 at 10%. As no formal decision for efficacy will be made based on these interim analyses, no overall alpha will be spent.

An independent DMC will be assembled to monitor safety data, efficacy data, and study conduct on a regular and ongoing basis during the study. See Section 10 for details regarding the alpha-spending plan and interim analyses conducted in this study.

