5.2. Treatment Groups

This is a randomized, double-blind, parallel treatment group design. Participants will be summarized by treatment groups. A participant randomized to the control group may make a crossover to the active treatment before Week 24 if the participant met the criteria for an early crossover. Unless specified, efficacy and safety analyses for between-treatment comparisons (parsaclisib + ruxolitinib vs placebo + ruxolitinib) will be conducted using the data truncated at the time of treatment crossover for those participants who made an early treatment crossover before Week 24. Data collected after the treatment crossover will be summarized and tabulated separately without treatment comparisons.

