7.3. Analysis of the Primary Efficacy Parameter

7.3.1. Primary Efficacy Analysis

The primary endpoint of this study is the proportion of participants with $\geq 35\%$ spleen volume reduction from baseline to Week 24 as measured by MRI (or CT scan in applicable participants). The primary endpoint will be analyzed by CMH test stratified by DIPSS category (intermediate-1 vs intermediate-2 vs high) and baseline (or screening, if applicable) platelet count ($\geq 100 \times 10^9/L$ vs 50 to $< 100 \times 10^9/L$ inclusive).

The baseline spleen volume will be measured by MRI (or by CT for applicable participants) during the baseline visit (Days -7 to 1); the last value will be used if there are multiple values measured during the baseline visit.

The Week 24 spleen volume will be measured by MRI (or by CT for applicable participants) during the Week 24 visit; the last value will be used if there are multiple values measured during the Week 24 visit. Missing values will not be imputed.

The percentage change from baseline to Week 24 will be calculated using the following formula:

$$\% \text{ change} = 100 \times [\text{Week 24 spleen volume} - \text{baseline spleen volume}] / \text{baseline spleen volume}$$

A participant will be considered as having achieved $\geq 35\%$ reduction of the spleen volume from baseline to Week 24, if the participant had both baseline and Week 24 spleen volume measurements, the participant did not make an early crossover to receive the active treatment (for ruxolitinib plus placebo participants) before the Week 24 visit, the percentage change from baseline was not missing, and the percentage change from baseline reduction was $\geq 35\%$.

A participant who had a missing Week 24 spleen volume, discontinued treatment before Week 24, or made an early crossover to receive parsaclisib plus ruxolitinib before the Week 24 visit will be considered as a nonresponder for the endpoint of $\geq 35\%$ reduction of spleen volume.

A participant who had a missing baseline assessment will be considered as nonevaluable.

At the time of interim analysis, a participant who was still on treatment, but has not followed up for the timepoint assessment and had no timepoint assessment, will also be considered as nonevaluable.

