7.4.2.3. Mean Change and Percentage Change in MFSAF v4.0 Total Symptom Score

The mean change and percentage change from baseline to Week X will be calculated using the following formula:

$$\% \text{ change} = 100 \times (\text{Week X total score} - \text{baseline total score}) / \text{baseline total score}.$$

The mean change and percentage change in TSS, the 7 individual scores, the total score of the 3 spleen-related symptom, including abdominal discomfort, pain under left ribs, and early satiety from baseline to Week X, will be summarized descriptively by treatment group and every 4 weeks using the ITT population. Missing values will not be imputed.

A plot of percentage change from baseline in MFSAF TSS at each visit will be provided.

7.4.2.4. Time to the First $\geq 50\%$ Reduction in Myelofibrosis Symptom Assessment Form v4.0 Total Symptom Score

The time to the first $\geq 50\%$ reduction in TSS is defined as the time from randomization to the first time participants had $\geq 50\%$ reduction in TSS. The daily TSS will be calculated according to the algorithm defined in Section 7.4.2.1.2. Participants with valid calculated baseline TSS and at least 1 postbaseline TSS who do not have $\geq 50\%$ reduction in TSS at the time of analysis will be censored at the time of the last valid calculated TSS. If the participants have no valid calculated baseline or postbaseline TSS, they will be censored at the date of randomization.

The stratified log-rank test will be used to compare time to the first $\geq 50\%$ reduction in TSS between 2 treatment groups in the ITT population at a 1-sided 2.5% significance level, stratified for baseline (or screening, if applicable) platelet count and DIPSS category. The strata identified in the randomization process will be used for the analysis.

Kaplan-Meier curves for time to the first $\geq 50\%$ reduction in TSS will be presented by treatment groups. The KM estimate of median time to the first $\geq 50\%$ reduction in TSS will be presented with its 95% CI. The 95% CI will be calculated using the generalization of method of Brookmeyer and Crowley (1982) with log-log transformation (Klein and Moeschberger 1997).

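### Time to first spleen or TSS response: censoring participants who die, stop treatment or cross over early makes the Kaplan-Meier curves and medians overstate actual response

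*SAP*

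**What the plan says.** **Spleen (SAP 7.4.1.1).** Participants without a "reduction in spleen volume at the time of analysis will be censored at the time of the last MRI or CT scan". For those lacking a scan, "If the participants have no baseline or postbaseline MRI or CT scan, they will be censored at the date of randomization".

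**TSS (SAP 7.4.2.4).** The rule is parallel: participants without a "reduction in TSS at the time of analysis will be censored at the time of the last valid calculated TSS", or at randomization if there is no valid baseline or postbaseline score.

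**Estimation and test.** Protocol Table 17 gives "Estimation: Kaplan-Meier" with a stratified log-rank test for both endpoints. The SAP adds a Kaplan-Meier median with its 95% CI and tests "at a 1-sided 2.5% significance level, stratified for baseline (or screening, if applicable) platelet count and DIPSS category". Of secondary endpoints outside the fixed sequence, SAP 3.2 says: "however, these are not considered alpha-controlled hypotheses".

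**Early crossover.** SAP 5.2 has between-arm comparisons "conducted using the data truncated at the time of treatment crossover for those participants who made an early treatment crossover before Week 24". The trigger in Protocol 4.1.3.1 is worsening symptoms plus a spleen volume increase of at least 25% over baseline. Participants unblinded on that trigger and found to be on parsaclisib must stop treatment.

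**After treatment stops.** Protocol Table 3 marks no MRI/CT at the EOT, safety follow-up or survival follow-up visits. Protocol 7.1.2 describes telephone contact for survival and later MF therapy.

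**Binary endpoint, for contrast.** In SAP 7.3.1 a participant who "discontinued treatment before Week 24, or made an early crossover to receive parsaclisib plus ruxolitinib before the Week 24 visit will be considered" a nonresponder. SAP 7.4.2.2 does the same for TSS.

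**The concern.** Kaplan-Meier treats a censored participant as having the same future chance of response as those still being scanned. That is reasonable for someone on treatment at the data cut-off. It is not reasonable for someone who has died, who has stopped treatment and has no further scan scheduled, or who was taken out of the comparison because the spleen grew. A participant who leaves before any postbaseline scan is censored at time zero and never enters the Week 12 risk set, although the analysis is labelled ITT.

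What is at stake is the descriptive summary. One minus Kaplan-Meier will be read as the probability of having responded, and the median as the time by which half the arm has responded. With this censoring they describe a hypothetical trial in which nobody leaves before response. If one arm loses more participants before response, its curve does not show that loss.

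**Working it through.** **Plan figures.** The plan states no power or expected probability for these endpoints, so there is no figure of their own to reproduce. I borrow two inputs from SAP 3.3: the normal-platelet response rates (41.0% and 58.2%) and the 5.3-year control median survival. The OS figure in that section reproduces closely by Schoenfeld's formula: Φ(√85/2 × |ln 0.54| − 1.96) = Φ(0.88) = 81.1%, against 80% stated. The response rates are proportions in response at Week 24. I use them only as anchors for the proportion ever responding by then.

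**Model.** Scans at Weeks 12 and 24.
- *h*: chance of response at each scan among those scanned and not yet responding.
- *D*: assumed chance of leaving before the Week 24 scan for someone who does not respond first; *s* = √(1 − *D*) per 12-week interval.
- Kaplan-Meier under the SAP rule: 1 − (1 − *h*)², which does not depend on *D*.
- Actual response (Aalen-Johansen): *s·h* + *s*²·*h*(1 − *h*).

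**Worked case.** True response 41.0%, *D* = 30%, so *s* = 0.8367. Solving 0.8367*h* + 0.70*h*(1 − *h*) = 0.410 gives *h* = 0.3108. Kaplan-Meier shows 1 − 0.6892² = 52.5%. The share leaving without response is 0.1633 + 0.8367 × 0.6892 × 0.1633 = 25.8%.

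| *D* by Week 24 | KM when true is 41.0% | KM when true is 58.2% | True response when KM reads 50% |
|---|---|---|---|
| 5% | 42.5% | 60.3% | 48.2% |
| 10% | 44.2% | 62.6% | 46.4% |
| 20% | 48.0% | 67.7% | 42.8% |
| 30% | 52.5% | 73.6% | 39.0% |

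The last column uses *h* = 1 − √0.5 = 0.293. It shows the median problem: Kaplan-Meier reaches 50% while 39.0% to 48.2% have responded.

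**Deaths alone.** At a 5.3-year median, 1 − exp(−ln 2/5.3 × 12/52.18) = 2.96% die per 12 weeks. A true 41.0% then reads 42.8%, and a true 58.2% reads 60.7%.

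**Longer follow-up.** Spleen scans continue past Week 24. With *h* = 0.293 and the same attrition over four scans, Kaplan-Meier reads 75% against an actual 67.3% (*D* = 10%) or 52.7% (*D* = 30%).

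**Two arms.** Simulation with 220 per arm, 4,000 runs, an unstratified log-rank and rejection at Z > 1.96 in favour of the higher-dropout arm.

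| Scenario | Dropout by arm | KM by arm | True response by arm | Log-rank rejects |
|---|---|---|---|---|
| Equal per-scan response | 5% vs 15% | 42.5% both | 41.0% vs 37.9% | 2.8% |
| Equal per-scan response | 10% vs 20% | 44.2% both | 41.0% vs 37.7% | 2.5% |
| Equal per-scan response | 10% vs 30% | 44.2% both | 41.0% vs 34.4% | 2.2% |
| Equal true response | 5% vs 15% | 42.5% vs 46.0% | 41.0% both | 11% |
| Equal true response | 10% vs 20% | 44.2% vs 48.0% | 41.0% both | 12% |
| Equal true response | 10% vs 30% | 44.2% vs 52.5% | 41.0% both | 38% |

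In the first three rows the test holds its 2.5% level (Monte Carlo standard error √(0.025 × 0.975/4000) = 0.25 points) and does not register the dropout difference. In the last three rows the per-scan response really does differ, so these rejections are not false positives for the cause-specific hazard. They would mislead only someone who read them as more participants responding.

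**The case against.** Several points stand and limit the finding.

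- **The test.** A reader might infer that the log-rank is biased as well. The simulation does not support that: with equal response among those scanned it keeps its level. Replacing it with Gray's test would change the question and depart from Protocol Table 17.
- **Hidden dropout.** A reader might infer that the plan conceals higher attrition in one arm. SAP 6.2 reports discontinuations with reasons by arm, SAP 9.2.3 tabulates TEAEs leading to discontinuation of each drug, and OS is analysed separately. Only these curves omit it.
- **Unequal dropout.** No dropout rate is given. The stopping rules in Protocol Table 11 are applied under blinding to parsaclisib and matching placebo alike. More stopping on parsaclisib is plausible from the risks in Protocol 2.6.1, but it is not documented.
- **Contradiction with the primary.** The primary asks who is in response at Week 24; time to first response asks something else. Different handling is not in itself an error. The fault is that the summary will be read as actual response.
- **Stakes.** Neither endpoint is alpha-controlled, and the planned outputs are curves and a median, not a stated Week 24 probability.
- **Diary.** Table 3 runs the TSS diary nightly to Week 24 with no treatment condition, so it is less clear than for scans that data end when treatment stops.
- **Redaction.** SAP text between 7.4.3 and 9 is redacted, so an exploratory competing-risk analysis there cannot be ruled out.

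None of this makes the planned curve or median an estimate of actual response.

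**Conclusion.** The concern holds for the Kaplan-Meier curves and medians in SAP 7.4.1.1 and 7.4.2.4. For 5% to 30% dropout by Week 24, the overstatement is 1.5 to 11.5 points on a true 41.0% and about 2 to 15 points on a true 58.2%. Deaths alone at the plan's control survival account for 1.8 and 2.5 points. For a true 41.0%, an apparent median by Week 24 needs dropout of about 25% or more: at *h* = 0.293, 0.293*s* + 0.207*s*² = 0.410 gives *s* = 0.868 and *D* = 1 − *s*² = 25%. If true response is close to half, much less suffices.

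These sizes rest on an assumed dropout range, a constant per-scan response chance and two scans. The direction does not depend on those values. Any between-arm effect is conditional on dropout that differs by arm, for which the documents give no figure. No confirmatory conclusion depends on this. It is worth correcting because the remedy is cheap.

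**What to change.** In SAP 7.4.1.1 and 7.4.2.4:

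1. Define death, permanent treatment discontinuation and early crossover, each before response, as competing events. State which drug's discontinuation counts, since Protocol 8.7 ties the EOT visit to stopping both. Keep ordinary censoring for participants still under assessment at the data cut-off.
2. Make Aalen-Johansen cumulative incidence curves by arm the descriptive summary, with the number of each competing event by arm beside them. A simpler route to the same quantity keeps these participants at risk as nonresponders to Week 24 for TSS and to the data cut-off for spleen.
3. Keep the stratified log-rank of Protocol Table 17, labelled as a cause-specific comparison among participants still under assessment.
4. Keep the censored Kaplan-Meier curves and medians as supportive.

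The cost is a little extra analysis with standard procedures and an entry in SAP 11.1, which now lists no changes to protocol-defined analyses. The curves will look slightly less favourable. No new data are needed.

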4.1.1. Study Schedule/Procedures

There will be study site visits and laboratory-only visits in the study.

Participants will have a regularly scheduled study site visit at screening, baseline, Day 1, and at the end of 2, 4, 8, 12, 16, 20, and 24 weeks of treatment (ie, visits designated Week 2, Week 4, and so on) and then every 12 weeks thereafter if continuing on treatment in the extension period. During these visits, assessments including blood samples and spleen measurements will be performed. All serology, lipid profile, and urinalysis laboratory assessments will be analyzed by a central laboratory. Serum chemistry, hematology, and coagulation parameters will be assessed using local laboratories. [REDACTED]

Participants will have laboratory-only visits to collect hematology laboratory samples at Week 6, Week 10, and, if continuing beyond Week 24, every 12 weeks beginning with Week 30. Participants may visit a local laboratory or a location convenient to the participant for these interim hematology assessments provided that the laboratory data and corresponding normal ranges can be scanned and e-mailed to the investigative site; interim laboratory visits at the study site laboratory are preferred. Additional and unscheduled laboratory assessments may be performed at investigator discretion, including following changes in dose, or if laboratory parameters are at Grade 3 or Grade 4 levels based on CTCAE v5.0.

Participants who cross over (defined in the following text) will have 2 additional study site visits: the day of crossover and 4 weeks after crossover. Participants who have crossed over will otherwise remain on the same study schedule they were on prior to crossover. Note these crossover participants may not need to have the laboratory visit at Week 30 as this may coincide with the Week 4 post-crossover visit.

Participants will have an MRI of the upper and lower abdomen and pelvis to determine the spleen volume at baseline, Week 12, Week 24, and every 12 weeks thereafter through Week 144. A CT scan will be substituted for participants who are not candidates for MRI or when MRI is not readily available. [REDACTED]

Participants will complete an electronic symptom diary (MFSAF v4.0) daily from baseline through the Week 24 visit (total of 25 weeks).

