5. STATISTICAL METHODOLOGY

5.1. General Methodology

Unless otherwise noted, SAS® software (SAS Institute Inc, Cary, NC; v9 or later) will be used for the generation of all tables, graphs, and statistical analyses. Descriptive summaries for continuous variables will include but not be limited to the number of observations, mean, standard deviation, median, minimum, and maximum. Descriptive summaries for categorical variables will include the number and percentage of participants in each category.

A participant randomized to the placebo group may cross over to parsaclisib treatment if the participant meets the criteria for an early crossover defined in Protocol Section 4.1.3. Unless specified, efficacy and safety analyses for between-treatment comparisons (parsaclisib vs placebo) will be conducted using the data truncated at the time of treatment crossover for those participants who make an early treatment crossover.

Interim analyses are planned for this study as defined in Section 10.

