7.4.1.2. Duration of Maintenance of a $\geq 35\%$ Reduction in Spleen Volume

The duration of $\geq 35\%$ reduction from baseline in spleen volume is defined as the interval between the first spleen volume measurement that is $\geq 35\%$ reduction from baseline and the date of the first measurement that is no longer a $\geq 35\%$ reduction from baseline. If the end date is not observed before the database cutoff, the duration will be censored at the last assessment.

The endpoint will be derived for participants who were randomized and who had at least 1 measurement of $\geq 35\%$ reduction from baseline.

Kaplan-Meier estimates of median duration with 95% CIs will be provided.

The ITT population with spleen volume response before crossover will be used.

A supportive analysis for duration of $\geq 35\%$ reduction from baseline in spleen volume defined as the interval between the first spleen volume measurement that is $\geq 35\%$ reduction from baseline and the date of the first measurement that is no longer a $\geq 35\%$ reduction from baseline that is also a $> 25\%$ increase from nadir will be provided.

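### Time to first spleen response (SAP 7.4.1.1) states no stop at crossover; the truncation rules in SAP 5.1 and 5.2 disagree with each other and do not expressly reach study-wide crossover

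*SAP*

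**What the plan says.** SAP 7.4.1.1 measures time from randomization to the first ≥35% reduction. A participant who has scans but no ≥35% "reduction in spleen volume at the time of analysis will be censored at the time of the last MRI or CT scan". The arms are compared by a stratified log-rank test "between 2 treatment groups in the ITT population at a 1-sided 2.5% significance level". The section does not mention crossover and gives no calendar cutoff.

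Two general rules apply unless something else is specified:

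- SAP 5.1 makes between-arm comparisons "using the data truncated at the time of treatment crossover for those participants who make an early treatment crossover". It cites Protocol 4.1.3, which allows early crossover both before Week 24 (4.1.3.1) and after it (4.1.3.2).
- SAP 5.2 applies the same truncation only "for those participants who made an early treatment crossover before Week 24". It then adds: "Data collected after the treatment crossover will be summarized and tabulated separately without treatment comparisons".

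Protocol 4.1.2 offers crossover to all placebo participants, subject to hematology criteria, once the last participant's Week 24 data are cleaned and frozen and the study is unblinded. Spleen imaging is scheduled "at baseline, Week 12, Week 24, and every 12 weeks thereafter through Week 144" (Protocol 4.1.1), so it continues after that crossover.

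For duration of response, SAP 7.4.1.2 states: "The ITT population with spleen volume response before crossover will be used".

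**The concern.** A placebo participant who has not responded by study unblinding may start open-label parsaclisib and go on being scanned. If a later scan shows a ≥35% reduction, SAP 7.4.1.1 taken alone records a placebo-arm event. The log-rank test and the placebo Kaplan-Meier curve would then credit placebo with responses reached on the experimental drug, and a real difference could be hidden.

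A smaller problem exists at any cutoff. A placebo participant who crosses over early but after Week 24 is truncated under SAP 5.1 and not under the truncation sentence of SAP 5.2. Two programmers could each follow the SAP and get different event counts.

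**Working it through.** **1. Which rule covers which crossover**

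| Crossover | SAP 5.1 | SAP 5.2, truncation sentence | SAP 7.4.1.1 |
|---|---|---|---|
| Early, before Week 24 (Protocol 4.1.3.1) | truncated | truncated | silent |
| Early, after Week 24 (Protocol 4.1.3.2) | truncated | not covered | silent |
| Study-wide (Protocol 4.1.2) | not covered | not covered | silent |

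The last sentence of SAP 5.2 could be read as covering all three rows. It directly follows a sentence about early crossover before Week 24, and it gives no censoring date. SAP 7.4.1.1 does give one, the last scan, and could be taken as the specified exception.

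**2. Can post-crossover scans exist?** Enrollment of 1.5 years (SAP 3.3) is 78 weeks. The last Week 24 visit is then at about 78 + 24 = 102 weeks after the first randomization. The first participant has 144 − 102 = 42 weeks of scheduled imaging left and the last has 144 − 24 = 120, less data-cleaning time. The OS analysis is expected at 3 years (156 weeks), about 156 − 102 = 54 weeks after the last Week 24 visit. At the Week 24 freeze itself, study-wide crossover has not begun.

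**3. The plan's own figure.** No power is stated for this endpoint. The nearest figure is the primary endpoint's 83.67% at N = 440, from rates of 58.2% (29.4%) versus 41.0% (17.2%) for normal (low) platelets. The low-platelet share is not given. With *n* per arm in a stratum and p̄ the mean of the two rates, the two-stratum CMH drift is Σ(n/2)(p₁ − p₀) / √[Σ(n/2)p̄(1 − p̄)]. At a 25% share (n = 165 and 55):

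- Numerator: 82.5 × 0.172 + 27.5 × 0.122 = 17.55.
- Denominator: √(82.5 × 0.2500 + 27.5 × 0.1787) = 5.05.
- Drift: 3.47.

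A fixed design then has 93.7% power (91.8–95.3% over shares of 50% down to 0). Requiring Z > 0.18 at 100, Z > 1.28 at 220 and Z > 1.96 at 440 participants, with the same effect at each look, gives 85.1%, 84.1%, 83.1% and 82.0% for shares of 0, 10, 20 and 30%. The stated 83.67% is reproduced within 2 points, so the same rates are used below.

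**4. Size of the effect (illustration).** Assumptions not in the documents:

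- 25% low platelets.
- 75% of Week 24 responses already present at Week 12; 2% new responses per later scan in both arms.
- Uniform accrual over 78 weeks.
- Study-wide crossover 8 weeks after the last Week 24 visit (week 110).
- All placebo nonresponders cross over, and no one drops out.
- Post-crossover responses appear at the first or second scan at least 6 weeks after crossover.
- Unstratified log-rank test; 600 simulated trials per setting.

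Rough check on the added events: the placebo Week 24 response is 0.75 × 41.0% + 0.25 × 17.2% = 35.05%, leaving 220 × 0.6495 ≈ 143 nonresponders. Mean time on study at crossover is 110 − 39 = 71 weeks, so about 3.4 later scans have passed, and 143 × 0.98^3.4 ≈ 133 remain. Post-crossover response in 10, 20 or 30% of them gives about 13, 27 or 40 events.

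| Data cut | Post-crossover response | Added placebo events | Mean Z, no stop | Power, no stop | Mean Z, censored at crossover | Power, censored |
|---|---|---|---|---|---|---|
| Week 24 freeze | 30% | 0 | 3.21 | 89% | 3.17 | 88% |
| 3 years | 10% | 12.6 | 2.13 | 57.5% | 3.14 | 89.3% |
| 3 years | 20% | 25.7 | 1.12 | 18.8% | 3.16 | 88.2% |
| 3 years | 30% | 38.8 | 0.31 | 5.7% | 3.13 | 87.3% |

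Power is the share of trials with Z > 1.96. The two Week 24 entries differ only by simulation noise.

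**The case against.** The strongest reply is that the plan already shows its intent. The last sentence of SAP 5.2 is not itself limited to early crossover. SAP 9.1 removes all post-crossover data from safety comparisons. OS has a crossover-adjusted sensitivity analysis (SAP 7.4.3). Where post-crossover responses are meant to count for placebo, as in the supportive analysis in SAP 7.3.3, the SAP says so. A reader might infer that the SAP is silent on post-crossover data; it is not. This stands as evidence of intent, but it leaves the text ambiguous and supplies no censoring date.

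The second reply is timing. Only OS has its own later trigger (85 deaths), and no section assigns a later cut to time to spleen response. If it is analyzed at the Week 24 freeze, early crossover is the only kind that can have happened, which may be why 5.1 and 5.2 name only that. This also stands. A reader might infer that the planned analysis loses most of its power; the documents do not support that. Nor do they exclude a later cut.

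Third, SAP 7.4.1.2 might be read as a rival definition of a placebo responder. It only selects who enters a duration analysis that has no between-arm test, and it does not censor duration at crossover.

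Fourth, the post-crossover response rate is unknown. The phase 2 add-on result in Protocol 2.6.1.4, 7 of 23 (30%), is for a ≥25% reduction in participants already on a stable ruxolitinib regimen. It does not fix the rate of ≥35% reduction from this study's baseline.

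**Conclusion.** The gap is one of specification. SAP 7.4.1.1 has no crossover stop, SAP 5.1 and 5.2 conflict on early crossover after Week 24, and neither expressly truncates efficacy data at study-wide crossover.

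At the Week 24 freeze, study-wide contamination is zero and the conflict touches few participants. At a later cut, the literal rule biases the comparison towards no difference. The direction is clear, but the size (about 13 to 39 added placebo events and mean Z of about 2.1 to 0.3 at 3 years) depends wholly on the assumptions listed, above all the post-crossover response rate. Dropout or incomplete uptake of crossover would reduce the number of added events.

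A reader might infer that a confirmatory claim is at risk. It is not: SAP 3.2 places this endpoint outside the alpha-controlled sequence, and the bias described runs against parsaclisib. It is still a listed secondary endpoint with a formal test, so the rule should be settled before unblinding.

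**What to change.** Three wording changes to the SAP:

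- **7.4.1.1, censoring:** *Participants with no earlier ≥35% reduction who cross over to open-label parsaclisib, whether early (before or after Week 24) or at study unblinding, are censored at their last scan on or before the first open-label dose. Responses after that dose are summarized separately.*
- **7.4.1.1, cutoff:** name the data cutoff for this endpoint, either the Week 24 freeze or a stated later cut.
- **5.1 and 5.2:** for spleen endpoints, use one shared phrase covering any crossover to open-label parsaclisib, and keep the supportive analysis in 7.3.3 as a named exception.

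No new data are needed, because SAP 4.1.2 already defines Day 1 of crossover. The cost is SAP wording and a small programming change. The statistical downside should be stated in the SAP: this censoring applies only to the placebo arm and may be informative. Early crossover requires spleen growth of at least 25%, so those censored early are probably less likely than others to have responded on placebo. Censoring them could therefore raise the placebo response estimate somewhat.
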